9. RANDOMIZATION AND MASKING

Randomization

A variable 2, 4, or 6 block randomization scheme will be generated the Johns Hopkins University Institute of Clinical and Translational Research. The scheme will entail two orders AB or BA consistent with our crossover design. Details of the block sizes will be concealed from study staff and investigators and generated prior to the study and placed in opaque, sealed envelopes. A designated staff member will open the envelope with the participant during the randomization visit after confirmation of eligibility and informed consent. This will be performed in a private location away from other staff. Once assigned order is revealed, this information will be shared with the study dietitian, who will provide instructions pertinent for each intervention phase. Order of intervention will not be shared with research technicians performing data assessments or with study investigators. Study personnel and investigators will not be unmasked until follow-up and all data collection are completed.

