12. ANALYSIS

The trial has sufficient resources to enroll 40 participants who will be randomly allocated to 1 of 2 sequences for each the two groups: (1) the SD group followed by the DD group or (2) the DD group followed by the SD group.

Power and sample size

Based on a cross-over trial design, using a variance of 1.71 at an alpha level of 0.05 with a power of 0.8, we estimated that we would need 41 participants to detect a change of -0.75 mg/dL between interventions.¹³ In two prior studies we had observed reductions of -1.3 and -1 mg/dL among subpopulations with a uric acid above 7 mg/dL.^{5,14}

Analysis Plan

This study is a randomized trial that tests the effects of an innovative intervention against a minimal intervention on a selected set of outcomes. The analysis will be conducted under the intent-to-treat principle for both the primary and the secondary endpoints. For the Primary Aim, groups will be compared using within-person differences in SUA levels. The analysis will be carried out with generalized estimating equations to compare 4-week SUA levels from both phases of the study, adjusted for baseline. This will allow us to test the null hypothesis that there is no difference in uric acid between the DASH diet intervention and the self-directed group (reference). Other outcome variables will be analyzed with a similar approach. For continuous outcomes, the distribution of outcome residuals will be assessed for normality and transformed where appropriate. Continuous outcomes will be analyzed via an identity function, while binary variables will be evaluated via a logit function.

Missing data

Based on the existing literature, we will employ recommended strategies to address missing data.⁷¹⁻⁷⁴ However, every effort will be made to collect outcome data on all participants.

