3.1 Randomization and primary analysis

Participants will be randomized using a computer-generated randomization scheme with varying sized blocks to 1 of 2 sequences in a 1:1 ratio such that approximately half of participants will undergo the DASH grocery intervention first followed by the self-directed phase while the other half will undergo the self-directed (reference) phase first, followed by the DASH grocery intervention. There is no washout period.

We will first confirm that the residuals of uric acid are normally distributed (if not these values will be log-transformed). We will then assess for carryover effects by: (1) examining a period variable in relation to uric acid (temporal effects) and (2) an intervention-by-period interaction term. If this is significant, we will conduct a period 1 only analysis (treating the trial as a parallel design), comparing the unpaired effects of 4-week DASH groceries on uric acid compared to 4 weeks of the self-directed group. This will be performed with linear regression adjusted for baseline uric acid values.

If there is not sufficient evidence of a carryover effect, we will compare serum uric acid measurements from both periods within person using the trial's crossover design. These comparisons will be performed with generalized estimated equations (normal distribution, identity function) with an exchangeable working matrix and robust variance estimator. These analyses will be adjusted for baseline uric acid measurements.¹

We will use an intent-to-treat approach for either of the two scenarios above.

Our hypothesis is that 4-weeks of the DASH grocery intervention will lower serum uric acid compared to 4-weeks of the self-directed diet. The null hypothesis is that there will be no difference in uric acid between either phases of the study.

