3.2 Power and sample size

Based on a cross-over trial design, using a variance of 1.71 at an alpha level of 0.05 using a twosided paired means test with a power of 0.8, we estimated that we would need 41 participants to detect a 4-week difference of -0.75 mg/dL between interventions.² In two prior studies we had observed reductions of -1.3 and -1 mg/dL among subpopulations with a uric acid above 7 mg/dL.^{3,4}

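### The crossover GEE lists no period term and no small-sample correction: about one point of test level for the primary outcome, more in small strata, and cheap to put right

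*SAP*

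**What the plan says.** SAP section 3.1 sets out two stages. The carryover check consists of "examining a period variable in relation to uric acid (temporal effects") and an intervention-by-period interaction; a significant result sends the trial to a period-1-only analysis. Otherwise the crossover comparison applies: "If there is not sufficient evidence of a carryover effect, we will compare serum uric acid measurements from both periods within person". The model is "generalized estimated equations (normal distribution, identity function) with an exchangeable working matrix and robust variance estimator", followed by "These analyses will be adjusted for baseline uric acid measurements". No other covariate is listed.

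Protocol section 12 agrees. It plans "generalized estimating equations to compare 4-week SUA levels from both phases of the study, adjusted for baseline" and mentions neither period nor a correction. It gives the size as "The trial has sufficient resources to enroll 40 participants".

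Protocol section 9 describes "A variable 2, 4, or 6 block randomization scheme" and names no stratification factor. The SAP's pre-specified stratified analysis repeats the primary analysis on seven criteria, with interaction terms. Section 3.5 plans GEE for the secondary outcomes, again with no stated period term.

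**The concern.** A crossover model without a period term leaves any shift between period 1 and period 2 in the residual variation. With equal sequences the diet estimate stays unbiased, but the standard error absorbs the shift and the test becomes conservative. With unequal sequences part of the shift also enters the estimate. Separately, an uncorrected sandwich variance is too small when there are few participants, and a normal reference adds to that. The two faults push the level in opposite directions, so the actual level depends on a period effect that nobody knows in advance.

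The SAP treats temporal effects as plausible enough to look for. It does not say whether period then enters the crossover model. At stake are a test level that is not fixed at 5%, two analysts fitting different primary models from the same text, and the reuse of the same test in much smaller groups.

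**Working it through.** **Inputs.** From the documents: N=40, 1:1 sequences, two-sided alpha 0.05, difference 0.75 mg/dL, variability 1.71. Assumed, because no document gives them: period effects p of 0 to 0.75 mg/dL, stratum sizes, dropout, normal data, and an uncorrected sandwich referred to 1.96.

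**1. The plan's own figure.** SAP section 3.2 reaches 41 participants "using a variance of 1.71 at an alpha level of 0.05 using a twosided paired means test".
- 1.71 as the SD of the difference: (1.960+0.842)² × 1.71² / 0.75² = 40.8, so 41.
- 1.71 as the variance of the difference: (1.960+0.842)² × 1.71 / 0.75² = 23.9, so 24.

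Only the SD reading gives 41. It is used below, with SD = √1.71 = 1.31 as the alternative.

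**2. Level with no period effect.** With complete pairs a person-level baseline does not alter the diet estimate. That estimate is the mean within-person difference, and its sandwich SE is √SS / N, where SS is the sum of squared deviations. This is √((N-1)/N) times the usual paired SE; at N=40, √(39/40) = 0.987, or 1.3% too small. The level is P(|t on N-1 df| > 1.96 × √((N-1)/N)).

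| n | Uncorrected | With an n/(n-1) factor |
|---|---|---|
| 40 | 6.0% | 5.7% |
| 20 | 7.1% | 6.5% |
| 10 | 9.6% | 8.2% |

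**3. Level with a period effect, 20/20.** The difference has mean δ+p in one sequence and δ-p in the other, so p² is added to the apparent variance but not to the true variance of the mean. At p=0.75 and SD 1.71 the SE is too large by about √(0.975 + 0.75²/1.71²) = √(0.975+0.192) = 1.08. Simulated results:

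| p (mg/dL) | Level, SD 1.71 | Power at -0.75, SD 1.71 | Level, SD 1.31 |
|---|---|---|---|
| 0 | 6.0% | 79.5% | about 6% |
| 0.25 | 5.8% | 79.0% | 5.6% |
| 0.5 | 5.0% | 77.3% | 4.5% |
| 0.75 | 4.0% | 74.5% | 3.1% |

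With period plus a pooled t on N-2 df, the level is 5.0% and power about 77% in every SD 1.71 row. Period alone, uncorrected, gives P(|t on 38 df| > 1.96 × √(38/40)) = 6.4%.

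**4. Bias.** Without a period term the shift is p × (n1-n2)/(n1+n2). Blocks of 2, 4 or 6 hold 40 participants to 21/19 at worst. At p=0.5:
- 21/19: 0.5 × 2/40 = 0.025 mg/dL (level about 5.0%).
- 20/16 complete pairs, if four dropouts all fell in one sequence: 0.5 × 4/36 = 0.056 mg/dL (level 5.6%).

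**5. Strata.** Sequences are not balanced within strata by design. At p=0.5, chance imbalance adds an error with mean zero and SD 0.14 mg/dL at n=10 (SE of the estimate 0.54), and 0.08 at n=20 (SE 0.38). Uncorrected two-group interaction tests run at 6.3% for 20/20, 6.6% for 25/15 and 7.9% for 30/10.

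**6. Coding of sequence.** If sequence is centred at its sample mean, the intercept is still the raw mean difference. At p=0.5 it is then biased by 0.5 × 4/20 = 0.10 mg/dL at 12/8 and 0.5 × 4/10 = 0.20 at 7/3. Coded +1/2 and -1/2, the intercept is the average of the two sequence means: the bias is zero and the level 5.0% at 20/20, 12/8 and 7/3.

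**7. Whole two-stage procedure.** Assumptions: only the interaction triggers the gate, at 0.05; within-person correlation 0.3 to 0.7; SD 1.71.

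| p (mg/dL) | As planned | With the fix |
|---|---|---|
| 0 | 8.1-8.4% | 7.1-7.5% |
| 0.5 | 7.0-7.4% | 7.0-7.4% |
| 0.75 | 6.1-6.7% | 7.0-7.6% |

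**The case against.** The strongest reply is that the change does little for the procedure actually planned. The carryover gate is the larger problem. With the fix the overall level stays near 7%, and at a 0.75 mg/dL period effect it rises, because a conservative test has been restored to 5%. This stands, and it limits the claim to the crossover test.

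The gate wording is also open. If a significant period term alone sends the trial to period 1, this would happen in roughly 47% of trials at 0.5 mg/dL and 80% at 0.75 (SD 1.71, 20/20). The whole-procedure figures above would then not apply, and the unconditional crossover figures at larger period effects would not describe the analysis as run. This stands too.

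The uncorrected sandwich and normal reference are inferred from silence. A software n/(n-1) factor lowers the levels but leaves them above 5%. The stratified analyses are exploratory, depend on the baseline distribution and allow categories to be combined. Testing seven factors without adjustment is a larger source of false positives than a level of 7% in place of 5%. These points lower the importance of the issue but do not remove it.

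A reader might infer that omitting period materially biases the primary result. The documents do not support that: it needs both a period effect and unequal sequences, and the blocks allow 21/19 at worst before dropout.

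**Conclusion.** The concern holds as a low-cost improvement to the crossover test. For the primary outcome the level departs from 5% by about one point in either direction at SD 1.71. At SD 1.31 it falls to about 3% if the period effect is 0.75 mg/dL. Bias is negligible at 21/19. The case is stronger in the strata, at about 7% for n=20 and 9.6% for n=10, where sequence imbalance also lets a period effect move the estimate.

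All of this rests on an uncorrected sandwich with a normal reference, and on assumed period effects and stratum sizes. A reader might also infer that the primary analysis is seriously invalid, or that a period term would bring it to 5%. Neither follows: the departure is small, period alone raises the level to 6.4%, and the gate remains.

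**What to change.** In SAP section 3.1, specify serum uric acid = diet + period + baseline, clustered by person, and name the small-sample correction and reference distribution in the same sentence. The two must be added together.

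- **Complete pairs.** Regress the within-person diet difference on sequence coded +1/2 and -1/2, not centred at the sample mean. Test the intercept with the ordinary pooled variance and t on n-2 df.
- **Other continuous analyses.** Use the same approach for continuous secondary outcomes, strata and interaction tests, with one df less for each further term.
- **Binary outcomes.** Add period to the GEEs in section 3.5. Their levels were not calculated here.
- **Sensitivity analysis.** Keep the model without period.
- **Scope.** State that this fixes the level of the crossover test only, and say which result, period or interaction, triggers the period-1 analysis.

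The cost is a short SAP amendment, one degree of freedom, and 2-3 points of nominal power at period effects of 0.25 mg/dL or less (79.0-79.5% to about 77%, SD 1.71). At 0.75 mg/dL the crossover test regains about 3 points of power. No new data are needed.

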3.2 Power and sample size

Based on a cross-over trial design, using a variance of 1.71 at an alpha level of 0.05 using a twosided paired means test with a power of 0.8, we estimated that we would need 41 participants to detect a 4-week difference of -0.75 mg/dL between interventions.² In two prior studies we had observed reductions of -1.3 and -1 mg/dL among subpopulations with a uric acid above 7 mg/dL.^{3,4}

3.3 Secondary Contrast

We will compare end of period uric acid with baseline values to determine baseline change in uric acid over each study period.

3.4 Pre-specified Stratified Analysis

We will repeat the primary analysis in subpopulations based on the following criteria:

1. Race (black vs white)
2. Stage II hypertension (>140/>90)
3. Obesity (BMI > 30 kg/m²)
4. Estimated glomerular filtration rate < 60 ml/min per 1.73 m²
5. Estimated Calorie intake (> vs ≤ median value)
6. Baseline uric acid 7-<8, 8-<9, 9-<10, ≥10 mg/dL (note categories may be combined to ensure a reasonable number in each group, given our small overall sample size)
7. Gout severity (based on number of flares at baseline, stratified by median value)

Interaction terms will be used to assess for effect modification by baseline characteristic. Note these analyses are contingent of the distribution of baseline characteristics.

Other stratified analyses based on baseline characteristics may be performed for hypothesis generation beyond the main study.

3.4 Sensitivity analyses

1. Models will be run with no adjustment for baseline uric acid
2. We will perform an on-treatment analysis: (i) persons who ate 25% or less of non-study foods during the DASH grocery intervention, (ii) persons whose estimated Calorie intake was met or exceeded by the food provided through the DASH grocery intervention, and (iii) persons who did not change antihypertensive medications or urate lowering therapies during the post-randomization study period
3. We will perform an analysis excluding women
4. Depending on whether there were carryover effects, we will perform the parallel (period 1 only) or crossover analysis as a sensitivity analysis.

4 Other outcomes

3.5 Secondary Endpoints

We will examine the effect of the diets on the following additional outcomes, testing the null hypothesis that there is no difference in the following outcomes between the self-directed (reference) and DASH diet intervention phases of the study. All these outcomes will be evaluated using generalized estimated equations to compare change between the 2 trial phases adjusted for baseline. We will examine the distribution of all variables. Model function will be based on the variable distribution whereby we will use linear regression for normally distributed outcomes and logistic regression for binomial outcomes. Continuous variables with non-normal residuals will be log-transformed with effects reported as a % change.

- A. Clinic blood pressure
 - Continuous variable, normal distribution
- B. Orthostatic hypotension
 - Binary variable, binomial distribution
- C. Timed Up and Go Test
 - Continuous variable, normal distribution
- D. Body mass index
 - Continuous variable, normal distribution
- E. Urinary sodium, potassium, and creatinine excretion
 - These may require log-transformation; anticipate continuous variables, normal distribution
- F. Self-reported fruit, vegetable, and fat consumption
 - These may require log-transformation; anticipate continuous variables, normal distribution
- G. Gout severity
 - Binary variables (severe vs not), binomial distribution
- H. Global physical function
 - Continuous variable, normal distribution
- I. Joint pain
 - Anticipate skewed scale that may require log-transformation
- J. Fasted LDL cholesterol

- Continuous variable, normal distribution

K. Fasting blood sugar

- Continuous variable, normal distribution

L. Urine pH and uric acid level

- Continuous variable, normal distribution

5 Missing data

We will employ a number of recommended strategies to prevent missing data:⁵⁻⁸

- A simplified data collection schedule that minimizes participant burden;
- Intention-to-treat analysis that includes following participants according to the data collection schedule regardless of compliance with the study intervention;
- Frequent engagement with the participants through visit reminder calls or notes;
- A 24-hour phone number that participants can contact for questions and support; □
 - Contiguous windows of time during which specific follow-up visits are allowed; □
 - Monetary incentives to encourage enrollment and continued participation;
- Rigorous training of clinic staff emphasizing the importance of:
 - Positive and warm interpersonal relationships between the participants and study staff
 - Study commitment during the consent process to ensure that potential participants understand the importance of completing the study
 - Addressing participant concerns to minimize dissatisfaction
 - Collecting data even if a participant discontinues the study treatment

Reasons for any drop-outs will be documented. If a drop-out occurs for reasons related to the study, i.e., informative censoring, we will perform sensitivity analyses using established methods for addressing informative censoring, namely, imputation techniques for missing data, best and worst-case scenarios, and use of the drop out event as a study end-point.⁹ We will review these approaches to minimize bias. Further, we will compare the baseline characteristics of participants with missing measures between the two assignments.

6 Safety outcomes

We will compare the rate of gout flares by assignment group using Poisson regression. We will also compare self-reported symptoms that are thought to potentially arise from the diets.

7 References

2. Senn SS. *Cross-over Trials in Clinical Research*. Second. John Wiley & Sons, Ltd; 2002.

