4. OVERVIEW OF DESIGN

This study will be an individual level, crossover RCT with 2 periods (**Figure**). The participants will be 40 adults with gout and hyperuricemia (≥ 18 years) who have SUA ≥ 7 mg/dL, who are not currently taking ULD. After informed consent, screening, and run-in, participants will be randomly assigned to each of two groups in random order: 1) Self-Directed (SD) vs. 2) DietitianDirected DASH Tailored (DD) with the provision of food. The primary outcome variable is SUA.

The duration of the intervention will be 4 weeks. Two screening visits will be used to determine interest and eligibility. The rationale for this timeline is that it is of sufficient duration to allow a complete effect of the intervention on uric acid to occur. Because it is not a prolonged period of intervention, the risk of non-compliance will be reduced, allowing for a better determination of the efficacy of the intervention. The DASH diet effects on SUA occur within 4 weeks and on blood pressure occur within 2 weeks, and are sustained from 2 weeks forward. As such, the 4 weeks will also provide sufficient time to see maximum diet effects on SUA and blood pressure and reduce the time period where recidivism is likely to occur.

Protocol visits for in-person data collection will occur during the screening period, at randomization, at week 4 after follow-up period 1 and follow-up period 2. At all protocol visits, our blinded data collectors will collect blood pressure and study questionnaires from participants in both arms of the study. Blood collection will be performed by phlebotomists blinded to the intervention arm.

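### With no washout, the planned two-phase BMI comparison is biased toward no effect if weight lost on DASH persists, and the SAP gives BMI no period-1 contrast to set beside it

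*SAP*

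**What the plan says.** SAP 3.1 states "There is no washout period" and randomises in "varying sized blocks to 1 of 2 sequences in a 1:1 ratio". Protocol section 4 sets the phase length ("The duration of the intervention will be 4 weeks") and justifies it for two outcomes: "The DASH diet effects on SUA occur within 4 weeks and on blood pressure occur within 2 weeks, and are sustained from 2 weeks forward". BMI is not mentioned there.

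For the secondary endpoints, BMI being entry D, SAP 3.5 says: "All these outcomes will be evaluated using generalized estimated equations to compare change between the 2 trial phases adjusted for baseline". Protocol section 12 describes the primary analysis as a GEE to "compare 4-week SUA levels from both phases of the study, adjusted for baseline", and adds: "Other outcome variables will be analyzed with a similar approach".

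SAP 3.1 sets out a carryover check on uric acid (a period term and an intervention-by-period term), with a period-1 regression if it is significant. Item 4 of the SAP's Sensitivity analyses provides for whichever of the period-1 and crossover analyses was not the main one, but it belongs to the primary-outcome chapter. SAP 3.5 repeats neither step for BMI.

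The schedule in Protocol section 7 has weight at SV2, RZ, FP1 and FP2, and height at SV2 only. FP1 closes the first phase, and the next assignment is explained at that visit.

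**The concern.** Weight accumulates. Going back to usual groceries does not at once restore weight lost in the previous four weeks, so the argument that four weeks is long enough for uric acid and blood pressure does not carry over to BMI. In the DASH-first sequence, the self-directed value is taken at FP2, four weeks after DASH ended. Whatever loss remains then lowers the reference value and shrinks the within-person difference. The self-directed-first sequence does not have this problem, so the pooled estimate mixes an undistorted difference with a shrunken one.

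Adjusting for baseline does not help. The same pre-randomisation value applies to both phases and cancels within the person.

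At stake is the estimate for aim D, the effect of DASH on BMI. It could be understated, with an interval centred on the wrong value, and nothing planned for BMI would show the reader that this had happened.

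**Working it through.** The plan states no effect size, variance or power for BMI, so there is no figure to reproduce. Its sample-size statement (41 participants, −0.75 mg/dL) concerns uric acid only.

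**Inputs from the documents:** two 4-week phases, no washout, 1:1 sequences, about 40 participants (20 per sequence), weight at RZ, FP1 and FP2. Height is measured once, so BMI changes only through weight.

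**Assumed, because the documents are silent:** DASH lowers weight by d over four weeks; the self-directed diet does nothing by itself; a share r of the loss remains four weeks after DASH, with r from 0 to 1. Where a scale is needed, d = 1 kg and the SD of 4-week weight change is 1.5 kg.

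**Planned comparison (DASH minus self-directed, end of phase)**
- Self-directed first: −d.
- DASH first: −d − (−rd) = −d(1 − r).
- 1:1 average: −d(1 − r/2).

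A period shift enters the two sequences with opposite signs and cancels. Carryover does not.

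**Period-1 contrast (FP1, DASH first versus self-directed first, adjusted for RZ)**
- Neither group has had an earlier phase, so the expectation is −d for every r.

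| r | Planned estimate, share of d | Period-1 contrast, share of d |
|---|---|---|
| 0 | 1.00 | 1.00 |
| 0.5 | 1 − 0.25 = 0.75 | 1.00 |
| 0.75 | 1 − 0.375 = 0.625 | 1.00 |
| 1 | 1 − 0.50 = 0.50 | 1.00 |

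**Check by simulation.** The planned GEE (exchangeable, robust, baseline-adjusted, n = 40, 150 runs per setting) returned 1.02, 0.74 and 0.52 of the true effect at r = 0, 0.5 and 1, with or without a period term. This used an assumed effect of −0.3 kg/m², a drift SD of 0.3 and a measurement SD of 0.15.

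**Precision with the 1.5 kg assumption**
- Planned: 1.5/√40 = 0.24 kg.
- Period-1: 1.5 × √(1/20 + 1/20) = 0.47 kg.

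With d = 1 kg, 20,000 simulated trials per r gave coverage of the planned nominal 95% interval of 94%, 81%, 66% and 48% at r = 0, 0.5, 0.75 and 1.

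**Would extending the uric acid carryover test to BMI be enough?** In the GEE simulation above, the intervention-by-period test was significant in about 25% of runs under full carryover, so it would usually miss it.

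**The case against.** **The wording is open.** Comparing change between phases could mean change from the weight at the start of each phase. SAP 3.5 does not say so, and Protocol section 12 points to end-of-phase levels, although it does not settle the matter. That reading would not rescue the estimate. The DASH-first difference becomes −d − (1 − r)d, and the average is −d(3 − r)/2: 150%, 125% and 100% of the true effect at r = 0, 0.5 and 1. It is right only with full persistence.

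**The protocol already limits carryover.** Section 10 keeps education light for that reason. This addresses learned behaviour, not weight already lost.

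**The planned estimate is more precise.** This stands. With d = 1 kg and SD 1.5 kg, its root mean squared error is √((r/2)² + 0.237²) = 0.34, 0.44 and 0.55 at r = 0.5, 0.75 and 1, against 0.47 for period 1. The plan is better on that measure until r is about 0.8. A reader might infer that a real weight loss would be reported as absent. The figures do not support this as a fault of the plan relative to the remedy. Approximate power, Φ(effect/SE − 1.96), is 88%, 75% and 56% for the plan at those r values, and 56% for period 1. The fault is an understated size, and the case is for reporting both estimates.

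**A sharper model might seem to avoid the trade-off.** One could model within-phase change with three exposure levels (self-directed before DASH, DASH, self-directed after DASH) and take DASH minus self-directed-before as the effect. Its standard error is 1.5 × √(1/40 + 1/20) = 0.41 kg and it does not depend on r. But its DASH changes come from both periods and its reference from period 1 only. An assumed period shift of 0.5 kg therefore moves it by 0.5/2 = 0.25 kg. Adding a period term reduces it to the period-1 contrast. It can serve as an exploratory result, not as the main one.

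**Conclusion.** The point holds as a conditional bias in one secondary outcome. If DASH lowers weight and some of the loss persists for four weeks, the planned BMI estimate is too small by a fraction r/2: 25% at r = 0.5, and 50% at r = 1. It would exceed half only if weight kept falling after DASH. If weight is fully regained, or DASH does not change it, there is no bias. Neither d nor r can be obtained from the documents, so no particular loss can be claimed, and one half is the limit under full persistence rather than an expected value.

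A reader might go on to infer that an understated BMI effect would make the uric acid reduction look independent of weight. The documents do not support that step. The SAP plans no weight-adjusted or mediation analysis of uric acid, and the protocol mentions mediating variables only for questionnaire data. BMI is one of twelve other aims and carries no power claim. The primary uric acid analysis is untouched.

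**What to change.** Under entry D of SAP 3.5, pre-specify two BMI results, both to be reported whatever any carryover test shows:

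1. The planned two-phase GEE, stating that it compares end-of-phase BMI and that it is biased toward no effect if weight loss on DASH persists into the self-directed phase.
2. The randomised period-1 contrast: FP1 BMI, DASH-first versus self-directed-first, by linear regression adjusted for BMI at RZ, with a 95% confidence interval.

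The three-level change model may be added as exploratory, with its assumption of no period effect on weight change stated.

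The cost is a few lines of SAP text and one regression on data already collected. The period-1 interval will be about twice as wide as the planned one (0.47/0.24 ≈ 2 under the assumed SD), so it may be inconclusive by itself. Its use is to show whether the two estimates differ in the direction that persistence predicts.
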